4.5.1 Initial Data Collection

Following the implant procedure (time zero), the following data will be collected and entered on the eCRFs while the pump is implanted:

- Two (2) hours post implant:
 - Vital signs (HR, BP, RR)
 - Fluid Ins and Outs since last reading
 - Hemodynamics
 - CVP
 - PA Systolic
 - PA Diastolic
 - PA Mean
 - PCWP
 - SvO2 as measured by the PA catheter
 - SaO2 as measured by pulse oximetry
 - Document any medication changes and adverse events
 - Urine labs per Appendix A
- Six (6) hours post implant and every 6 hours for 24 hours post implant:
 - Vital signs (HR, BP, RR)
 - Fluid Ins and Outs since last reading
 - Hemodynamics
 - CVP
 - PA Systolic
 - PA Diastolic
 - PA Mean
 - SvO2 as measured by the PA catheter
 - SaO2 as measured by pulse oximetry
 - Document any medication changes and adverse events
- Twelve (12) hours post implant and every 12 hours until Pump retrieval:
 - Blood and urine labs per Appendix A
- Twenty-four (24) hours post implant and every 24 hours until Pump retrieval:
 - Cardiovascular exam (edema, pulmonary auscultation, weight)
 - Vital signs (HR, BP, RR)
 - Fluid Ins and Outs since last reading
 - Hemodynamics
 - CVP
 - PCWP
 - PA Systolic
 - PA Diastolic
 - PA Mean
 - SvO2 as measured by the PA catheter
 - SaO2 as measured by pulse oximetry

- Dyspnea evaluation
- Document any medication changes and adverse events
- Blood labs per Appendix A

BMI will be calculated by the sponsor. Patient should be maintained on anticoagulation and antiplatelet therapy per **Appendix B**.

If the Aortix Pump is suspected to be malfunctioning or mal-positioned, imaging studies, diagnostic procedures, or access site exam may be performed as needed.

Prior to any unplanned retrieval of the Aortix Pump, hemodynamic and laboratory assessments should be repeated, and a fluoroscopic image of the pump position should be taken, and the image documented.

Refer to **Appendix A** for a detailed study monitoring schedule.

4.5.2 Programming the Aortix Pump/Pump Speed Changes:

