4.5.3 Congestion Target Met/Therapy Deemed Ineffective Data Collection

Once the congestion target has been met or therapy has been deemed ineffective, before weaning begins, the following assessments should be made within 12 hours of beginning weaning:

- Cardiovascular exam (edema, pulmonary auscultation, weight)
- Vital Signs (HR, BP, RR)
- Dyspnea evaluation
- Fluid Ins and Outs since last reading
- Hemodynamics:
 - CVP
 - PA Systolic
 - PA Diastolic
 - PA Mean
 - PCWP
 - SvO2 as measured by the PA catheter
 - SaO2 as measured by pulse oximeter
- Echocardiogram
- Blood and urine labs per Appendix A
- Document any medication changes and adverse events

If the congestion target timepoint overlaps with a scheduled assessment (e.g, an every 24 hour hemodynamic measurement), the scheduled assessment value can be used and also entered on the congestion target met timepoint eCRF.

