5.3 Risk Mitigation

In addition, this protocol provides steps to mitigate risk to study patients. These include the following:

- Limited Study Size: A limited number of patients will receive the Aortix Pump in this study to determine performance and safety.
- Treatment Duration: The Aortix Pump will only remain implanted up to the point the investigator determines therapeutic goals have been reached. Alternatively, if the investigator determines Aortix Pump therapy is ineffective or unsafe, Aortix Pump may be retrieved at any time.
- Follow-up Assessments: Patients will be monitored closely for device performance, effectiveness, and adverse events.
- Investigator Selection: The investigators in this study are selected based on their experience in performing large bore cardiovascular interventional procedures and experience treating patients with ADHF with worsening renal function.
- Site Selection: Study sites will have sufficient expertise and resources to manage adverse events and provide appropriate alternative therapies if needed.
- Investigator Training: Investigator(s) will be trained in proper device operation prior to study start. Training will include didactic and hands-on training with the Aortix System.
- Subject Screening: The study protocol includes appropriate precautions in patient selection. For example, patients with known anatomic incompatibilities, significant co-morbidities or uncontrolled cardiovascular or other disease will be excluded.
- Adverse Event Monitoring: Timely detection, treatment, and reporting of all adverse events.
- Adverse Event Monitoring: Enrollment pause based on occurrence of procedural related death or serious procedural related adverse events (see Section 6).
- Independent Safety Monitoring. Use of an external clinical events committee for safety monitoring with timely adjudication of adverse events.

6. Adverse Events

Adverse event definitions used in the study are based on ISO 14155:2011 (Clinical Investigation of Medical Devices for Human Subjects – Good Clinical Practice) as defined below. Specific definitions of key Adverse Events are listed in **Appendix C: Key Adverse Event Definitions**. The Clinical Event Committee may elect to further modify or add to the definitions.

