Appendix A: Schedule of Visits and Procedures

Category	Pre-Therapy		Aortix Therapy								Post-Therapy			
	Pre-Implant Period (Baseline Monitoring)	Day of Implant (Pre-implant)	Implant to Pump Retrieval					Once Congestion Target is Met and Within 12 hours of Beginning Weaning ^α	Day of Pump Retrieval (Pre-Pump Retrieval)	Cath-Lab Pre-Pump Retrieval	Post-Pump Retrieval Monitoring		Follow-Up: 30 days (± 7 days) from Pump retrieval	
	Current hospitalization once	once	Once (after pump deployed)	2 hours post implant ⊕ (± 30 min)	6 hours post implant (± 30 min) and Every 6 hours (± 1 hour) for 24 hours post implant	Every 24 h (± 2 hours)◆	Pump Speed Changes #	once	once	once	Every 24 h (± 2 hours)	Once at 72 hours post retrieval (± 4 hours) or discharge (whichever is earlier)	once	
Informed Consent ¹	X													
Med History	X													
NYHA Class	X											X	X	
Cardiovascular exam (edema, pulm auscultation, weight)	X	X				X		X				X	X	
Vital Signs: HR, BP, RR #	X	X		X	X	X	X	X		X		X	X	
Height	X													
Fluid Ins and Outs*		X*		X	X	X	X	X		X	X ^β			
Dyspnea Evaluation		X				X		X				X	X	
KCCQ, EQ5D	X												X	
HEMODYNAMICS														
CVP, PAP #		X		X	X	X	X	X		X				
PCWP #		X		X		X	X	X		X				
SvO ₂ , SaO ₂ **		X		X	X	X		X		X				
IMAGING														
Anatomy Screening	X													
Echo	X							X						
Fluoro Image			X							X				
MEDICATIONS	X		Record all cardiovascular/renal medications and medication changes.****										X	
OTHER EVENTS***			Record all adverse events, readmissions and mortality.											

1 Patient must sign informed consent before undergoing PA catheter placement for verification of inclusion criteria for objective measure of congestion or before undergoing imaging to assess anatomy for exclusion criteria for contraindicated anatomy.

α One time assessments to be taken once congestion targets are met or therapy has been deemed ineffective (decision has been made to retrieve device). These assessments should be performed before the pump speed is turned down; within 12 hours of beginning weaning.

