7.8.3 Primary Effectiveness

Primary Effectiveness analysis will be performed for As-Treated population to include:

- Percentage of patients with clinically significant decongestion as measured by the PA catheter compared to the total number of patients in the As-Treated population;
- Percentage of patients with a decrease in CVP or PCWP of $\geq 20\%$ from pre-implant until congestion target is met or therapy deemed ineffective compared to the total number of patients in the As-Treated population;
- Change in Urine Output Assessed as the hourly rate of urine output before pump placed vs hourly rate of urine output over the Aortix therapy period until either congestion target met or therapy is deemed ineffective for patients within As-Treated population;
- Percentage of patients with a decrease in BNP or NT-pro-BNP of $\geq 20\%$ from pre-implant until congestion target is met or therapy deemed ineffective with respect to the total number of patients within the As-Treated population.

Descriptive summary of percentages will be provided for device performance analysis variables. Corresponding listings will be provided for As-Treated populations.

In addition, effectiveness measurements (CVP, PCWP, BNP and NT-pro-BNP) collected Day of Implant (Pre-implant) and Once Congestion Target Met will be compared using non-parametric Wilcoxon Signed-Rank by subgroup and overall for those patients within As-Treated populations that have the effectiveness measurements available at both timepoints.

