7.9.5 Hemodynamic parameters

Hemodynamic parameters, including measurements of CVP, PCWP, SaO₂, SvO₂ and PA Pressure (Systolic, Diastolic and Mean) will be listed for As-Treated and PSC populations.

Summary of CVP, PCWP and PA Pressure (Systolic, Diastolic and Mean) at Baseline and Once Congestion Target is Met will be provided along with the summary of change from Baseline to Once Congestion Target for As-Treated and PSC populations.

Measurements of CVP, PCWP and PA Pressure (Systolic, Diastolic and Mean) collected starting from the time of implant will be presented graphically for each patient and each parameter for As-Treated and PSC populations.

Boxplots of CVP and PCWP will be provided by subgroup and overall to compare baseline results with Congestion Target Met and Retrieval (defined as the last non-missing measurement collected during Aortix Therapy) for As-Treated population.

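### The supplementary signed-rank tests and the hemodynamic change summary can lose patients who leave pump support without the pre-weaning visit, which can favour the device

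*SAP*

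**What the plan says.** After the primary percentages, SAP 7.8.3 adds a comparison of CVP, PCWP, BNP and NT-pro-BNP values "collected Day of Implant (Pre-implant) and Once Congestion Target Met". They "will be compared using non-parametric Wilcoxon Signed-Rank by subgroup and overall", in As-Treated patients "that have the effectiveness measurements available at both timepoints". No rule covers a missing second value. These are the only hypothesis tests named in either document, and their output (Table 14.2.1.3.2) is titled as As-Treated. SAP 7.9.5 summarises change in CVP, PCWP and PA pressure to the same second timepoint.

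The protocol defines that visit more broadly than the SAP label suggests. Section 4.5.3 says that, before weaning, "the following assessments should be made within 12 hours of beginning weaning". The Appendix A footnote reads: "One time assessments to be taken once congestion targets are met or therapy has been deemed ineffective (decision has been made to retrieve device".

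Therapy can also end in other ways. Protocol 4.5 lists a need for escalated therapy and device safety concerns among the reasons to stop, and 5.3 says that "if the investigator determines Aortix Pump therapy is ineffective or unsafe, Aortix Pump may be retrieved at any time". For such cases 4.5.1 provides a separate assessment: "Prior to any unplanned retrieval of the Aortix Pump, hemodynamic and laboratory assessments should be repeated". Appendix A also schedules CVP and PCWP daily and BNP or NT-pro-BNP every 12 hours on the pump, and all of them again in the cath lab before retrieval.

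The SAP has two fallback conventions, and neither reaches the tests. In 7.9.5 the CVP and PCWP boxplots include "Retrieval (defined as the last non-missing measurement collected during Aortix Therapy". In 7.14 the last pre-retrieval timepoint replaces Congestion Target Met for urine output only, on the ground that the latest CRF does not collect that timepoint.

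**The concern.** The pre-weaning visit presupposes a wean. A patient whose pump is removed abruptly for a safety event, device failure or escalation, or who dies on support, may never have it. That patient then leaves the tests and the change summary even when usable on-pump readings exist. If such patients did worse than the rest on pressures or natriuretic peptide, the p-values and the average change describe a favourable subset under an As-Treated title. SAP 2.3 says the study will provide initial evidence of safety and effectiveness and input to later designs, so an inflated change could be carried into the next trial's assumptions.

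**Working it through.** **Plan's own figure.** There is none for these tests: no power, effect size, alpha or expected early-retrieval count. SAP 2.3 says the sample size of up to 30 implanted patients was not statistically derived.

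**Who has a second value.**

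| How therapy ends | Pre-weaning visit expected? | Other on-pump reading |
|---|---|---|
| Target reached | Yes (Protocol 4.5.3) | Scheduled readings |
| Judged ineffective | Yes (4.5.3, Appendix A footnote) | Scheduled readings |
| Safety event, device failure or escalation, no planned wean | Not assured | 4.5.1 assessment; scheduled readings |
| Death on support | Not assured | Scheduled readings up to death |

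Only the last two rows are at risk.

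**Effect on the tests.** Assumptions: 30 treated patients, true change zero, changes X standard normal with positive meaning worse, two-sided 5% level. A selection score S = ρX + √(1 − ρ²)·Z, with Z independent standard normal, decides who is lost: the k patients with the highest S. The test runs on the remaining m = 30 − k, with W the sum of ranks of |X| over positive changes:

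z = [W − m(m+1)/4] / √[m(m+1)(2m+1)/24], reject if |z| > 1.96.

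Results from 40,000 simulated trials per setting, as false-positive rate with the spurious mean change in brackets:

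| Lost (k) | ρ = 0 | ρ = 0.5 | ρ = 1 |
|---|---|---|---|
| 0 | 4.9% | 4.9% | 4.9% |
| 3 | 4.9% (0) | 7.7% (−0.09 SD) | 17.4% (−0.19 SD) |
| 6 | 5.0% (0) | 13.5% (−0.17 SD) | 45.5% (−0.34 SD) |

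Testing all 30 patients gives about 5% throughout. The values of k and ρ are assumptions.

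**Effect on the change summary.** Suppose 3 or 6 of 30 leave early with no change and the others fall 25%. The mean in patients with both values is −25%. In all treated patients it is [27 × (−25) + 3 × 0]/30 = −22.5%, or [24 × (−25) + 6 × 0]/30 = −20%. The median is −25% either way. The standard signed-rank test discards zero differences, so its result would not change in this scenario. The tests are distorted only if the lost patients had non-zero changes that were worse than the rest.

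**Responder percentages.** SAP 3.2 uses non-missing denominators unless stated otherwise, and 7.8.3 does state otherwise: all As-Treated patients. With an assumed 18 responders the reported rate is 18/30 = 60.0% however many values are missing. A complete-case rate would have been 18/27 = 66.7% or 18/24 = 75.0%. The specified denominator prevents that rise.

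**The case against.** A reader might infer that early failures as a group vanish from the primary effectiveness results and that benefit is therefore overstated. The documents do not support this. Failures declared ineffective have the same visit as successes, and the footnote's reference to a decision to retrieve may reach further still. The tests are supplementary to the responder percentages, and urine output already runs to the last pre-retrieval reading (SAP 7.8.3.1).

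There is more on that side. This is a feasibility study without a stated hypothesis, and Protocol section 7 says each patient's data will be reviewed individually. The CVP and PCWP boxplots, individual plots and listings let a careful reader see what the tests omit. The direction of bias is not established either: a patient retrieved for bleeding or hemolysis may have decongested well. Section 4.5.1 says the readings should be repeated, so they are not guaranteed.

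Substitution has its own limits. The boxplot definition of Retrieval can pick up a cath-lab reading taken after the speed has been reduced (Protocol 4.5.4 and 4.6.1), whereas the planned visit precedes any reduction. It is not defined for BNP. For a death on support, a carried-forward pressure does not represent the outcome.

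All of this narrows the point and shapes the remedy. It does not supply a rule for the patients in the last two rows of the first table, and plots do not correct a p-value or a mean change computed without them.

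**Conclusion.** The concern holds in a limited form. The complete-pair rule in SAP 7.8.3, and the change summary in 7.9.5, can exclude patients who leave support without a planned wean or who die on it, and this can favour the device. It is a stated rule with a possible bias, in tests that are secondary to the responder percentages.

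The size cannot be fixed from the documents. For 3 to 6 of 30 patients lost, with ρ between 0.5 and 1 and no true change, the false-positive rate is 7.7% to 45.5% against about 5%. At ρ = 0 there is no inflation. The upper end is an extreme, in which exactly the worst changes are lost.

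A further inconsistency bears on this. If SAP 7.14 is right that the latest CRF does not collect the timepoint, the tests in 7.8.3 may lack a second value for many patients, not only for early exits. Yet Appendix 1 still plans a listing of the congestion target (16.2.6.4). The documents do not settle which is meant.

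**What to change.** In SAP 7.8.3 and 7.9.5:

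- Define the second timepoint as the visit made either when the congestion target is reached or when therapy is judged ineffective, matching Protocol 4.5.3.
- Where that value is missing, use the last on-pump CVP, PCWP and BNP or NT-pro-BNP taken before any weaning speed reduction, including the assessment before an unplanned retrieval. Do not reuse the boxplot definition unchanged, since it can include readings at a reduced speed and omits BNP.
- Keep the both-timepoints analysis as a sensitivity analysis.
- Report how many patients were substituted or excluded, with reasons, and show deaths on support separately.
- Reconcile 7.8.3 with the statement in 7.14 about the latest CRF.

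The cost is SAP wording and one derived variable, built from readings the protocol already schedules. The results may be slightly less favourable.

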7.8.3.1 Fluid Intake / Urine Output

Cumulative Fluid Intake / Urine Output (mL) will be analyzed starting from the baseline measurement until Aortix retrieval. At each post-implant timepoint cumulative Fluid Intake / Urine Output (mL) will be defined as the total sum across all timepoints until corresponding post-implant timepoint. Cumulative Net Loss (mL) will be defined as the difference between Urine Output and Fluid Intake. Cumulative Fluid Intake, Urine Output and Net Loss will be presented graphically measurement from the baseline until Aortix retrieval by patient for As-Treated and PSC populations.

Hourly rate (mL/h) of Fluid Intake / Urine Output / Net Loss during Aortix therapy will be defined as cumulative Fluid Intake, Urine Output and Net Loss from baseline till the last pre-retrieval timepoint available divided by the number of hours (h) from baseline timepoint measurement till the last pre-retrieval timepoint available.

Baseline hourly rate (mL/h) of Fluid Intake / Urine Output / Net Loss will be defined as of Fluid Intake / Urine Output / Net Loss ([Urine Output] - [Fluid Intake]) from the last pre-baseline measurement to baseline divided by the number of hours (h) from the corresponding last pre-baseline timepoint till baseline.

Hourly rate of Fluid Intake / Urine Output / Net Loss at Baseline, during Aortix therapy and corresponding change from Baseline will summarized with descriptive statistics for As-Treated population.

Boxplots of Hourly rate of Fluid Intake / Urine Output / Net Loss will be provided by subgroup and overall to compare hourly rate during Baseline with hourly rate during Aortix therapy for As-Treated population.

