3.3.3 Primary Effectiveness Endpoints

1. Clinically significant decongestion as measured by the PA catheter. Decrease in CVP or PCWP of $\geq 20\%$. [timeframe: pre-implant vs when congestion target is met or therapy deemed ineffective].
2. Change in Urine Output Assessed as the hourly rate of urine output before pump implanted vs hourly rate of urine output over the Aortix therapy period (until congestion target met or therapy deemed ineffective)
3. Decrease in BNP or NT-pro-BNP by 20% (pre-implant vs when congestion target is met or therapy deemed ineffective)

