4.5.2.1 Programming the Pump

The Aortix Pump should initially be operated at a speed of 25 krpm for a minimum of two days. The pump may be stopped once congestion and hemodynamic targets have been achieved for that patient as assessed by the investigator. The pump should be left in place for a sufficient time to achieve the diuresis and hemodynamic goals for the patient. All adjustments are at the discretion of the investigator according to their clinical judgement. Once congestion and hemodynamic targets have been achieved, diuretic or other therapies may be down titrated or discontinued, at the physician's discretion, but the pump should be kept running at 25 krpm. **If a decision is made to reduce the Pump speed, vital signs, hemodynamic measurements and fluid ins and outs must be recorded before speed reduction in accordance with Appendix A.**

If congestion and hemodynamic targets have not been achieved after 2 days, the pump speed may be turned up in 1 krpm increments to see if running the pump at a higher speed will provide benefit to the patient.

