4.5.4 Weaning the Pump Speed

Once the decision has been made to cease therapy, the pump speed may be adjusted down gradually (in increments of 2-5 krpm) while monitoring the patient's hemodynamics and urine output. The pump speed may be reduced to 18-20 krpm before it is retrieved. This process should ideally be conducted over a **minimum timeframe** of three hours with a minimum of two hours to reduce the speed to 18-20 krpm and a minimum of one hour of observation of the patient before removal. Only once in the cath lab and ready for retrieval should the Pump be turned OFF.

Figure 2 summarizes the pump programming steps.

[figure not shown]

Figure 2: Pump Programming

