7.14 Changes to Analyses Specified in Protocol

At the time of this SAP preparation, the following changes have been made to analyses specified in the protocol:

- The protocol specifies analysis of change in Urine Output Assessed as the hourly rate of urine output before pump implanted vs hourly rate of urine output over the Aortix therapy period until congestion target met or therapy deemed ineffective. But timepoint “Once Congestion

Target Met” is not collected in the latest CRF. Due to that, the last pre-retrieval timepoint available is used instead of the Congestion Target Met timepoint.

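### The SAP ends the on-therapy urine-output window at the last pre-retrieval reading, so in weaned patients hours beyond the protocol's end point count as therapy

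*SAP*

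**What the plan says.** **The endpoint.** Protocol 3.3.3 sets the hourly urine output before implant against the rate on therapy, and closes the therapy period when the congestion target is reached or the therapy is judged not to work. SAP 7.8.3 keeps that end point: "hourly rate of urine output over the Aortix therapy period until either congestion target met or therapy is deemed ineffective".

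**When that moment is recorded.** Protocol 4.5.3: "Once the congestion target has been met or therapy has been deemed ineffective, before weaning begins, the following assessments should be made within 12 hours", counted back from the start of the wean. The list includes "Fluid Ins and Outs since last reading". Note α in Appendix A places the same assessments before the speed is lowered.

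**The formula.** SAP 7.8.3.1 computes the therapy rate as the cumulative amount "from baseline till the last pre-retrieval timepoint available divided by the number of hours (h) from baseline timepoint measurement till the last pre-retrieval timepoint available". SAP 7.14 declares this as a change from the protocol: "the last pre-retrieval timepoint available is used instead of the Congestion Target Met timepoint". The reason given is that the latest CRF does not collect the target-met timepoint.

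**What lies between the two end points.** Protocol 4.5.4 allows the speed to be stepped down once therapy is to stop, ideally over three hours or more: "a minimum of two hours to reduce the speed to 18-20 krpm and a minimum of one hour of observation of the patient before removal". Protocol 4.6.1 then schedules a fluid reading in the cath lab, at whatever speed the pump is running, just before it is switched off.

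**Another reading before weaning.** Protocol 4.5.2.1 says that when speed is to be reduced, "vital signs, hemodynamic measurements and fluid ins and outs must be recorded before speed reduction in accordance with Appendix A". Appendix A marks fluids in its Pump Speed Changes column.

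**The concern.** SAP 7.8.3 and 7.8.3.1 give two different windows for one primary effectiveness endpoint, and the section with the formula is the one that will be programmed. Its window takes in hours of a different kind: time at reduced speed, and any wait between the target-met assessment and the start of weaning.

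The amount added varies by patient. Someone retrieved without a wean contributes no weaning hours, while someone with a short course contributes proportionally the most. If urine output falls as support is withdrawn, the estimated change is pulled towards no effect, and most strongly in the quickest responders. The protocol and SAP both say that the study's data will feed the design of later studies, so the definition matters even though the analysis is descriptive.

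**Working it through.** **1. The stated figure.** Protocol 4.5.4 gives 2 h of speed reduction plus 1 h of observation = 3 h, which matches its stated minimum.

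**2. Formula.** Let T be the hours from the baseline reading to the target-met assessment, g the hours from that assessment to the start of weaning (0 to 12, protocol 4.5.3), and W the weaning hours. The baseline reading is taken as coinciding with pump start. With r for the urine rate in each stretch:

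- SAP rate = (T·r_T + g·r_g + W·r_W)/(T + g + W); protocol rate = r_T.
- Share of the denominator outside the protocol window = (g + W)/(T + g + W).
- Share at reduced speed = W/(T + g + W).

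**3. Shares.** T = 48 h is the two-day minimum at 25 krpm (protocol 4.5.2.1). A total of 168 h is the 7 days for which the pump was tested (protocol 4.5). W = 3 h throughout.

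| T (h) | g (h) | At reduced speed | Outside protocol window |
|---|---|---|---|
| 48 | 0 | 3/51 = 5.9% | 5.9% |
| 96 | 0 | 3/99 = 3.0% | 3.0% |
| 165 | 0 | 3/168 = 1.8% | 1.8% |
| 48 | 12 | 3/63 = 4.8% | 15/63 = 23.8% |
| 96 | 12 | 3/111 = 2.7% | 15/111 = 13.5% |
| 153 | 12 | 3/168 = 1.8% | 15/168 = 8.9% |

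**4. Effect on the estimate.** The documents give no urine rates. Assume 100 mL/h at baseline and 150 mL/h on therapy, so the protocol change is +50 mL/h.

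- T = 48, W = 3, output back to 100 during the wean: (48·150 + 3·100)/51 = 147.1, change +47.1 (5.9% lower).
- The same, but output falls only to 125: (48·150 + 3·125)/51 = 148.5, change +48.5 (2.9% lower).
- T = 165, W = 3, back to 100: (165·150 + 3·100)/168 = 149.1, change +49.1 (1.8% lower).
- T = 48, g = 12, W = 3, output holds at 150 during the wait and is 100 during the wean: (60·150 + 3·100)/63 = 147.6, change +47.6 (4.8% lower).
- The same, but already at 100 throughout the wait: (48·150 + 15·100)/63 = 138.1, change +38.1 (23.8% lower).
- Output unchanged after the assessment: no difference. If it rises, the change is inflated.

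**5. The stated reason, set beside the rest of the documents.** SAP 7.14 says the target-met timepoint is not in the latest CRF. Against that:

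- Protocol 4.5.3 refers to an eCRF for this timepoint.
- SAP 7.8.3 tests CVP, PCWP and the natriuretic peptides at it.
- SAP 7.9.2, 7.9.3 and 7.9.5 summarise laboratory values, vital signs and hemodynamics at it.
- Listing 16.2.6.4 is devoted to the congestion target.

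SAP 7.14 may mean only that the fluid field is missing there. Even so, protocol 4.5.2.1 and Appendix A call for a fluid reading tied to speed changes, which lies nearer the protocol's end point than the cath-lab reading does.

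**The case against.** **Disclosure.** A reader might infer that the endpoint was altered without notice. It was not: SAP 7.14 states the change and gives a reason. Disclosure does not take the extra hours out of the rate, however, nor does it reconcile SAP 7.8.3 with 7.8.3.1.

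**Data availability.** A reader might also infer that a pre-wean fluid value is certainly in the database, so that the substitution was unnecessary. The documents do not show this. The SAP was written against a CRF dated January 2022 that is not among them, and a protocol requirement does not prove a CRF field. Appendix A's timing note for speed changes covers heart rate and pressures, not fluids. What can be said is that such a reading is required.

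**Size.** Losses of a quarter or more are a tempting headline. They need a 12 h wait during which output has already returned to baseline, although the pump is still at full speed. Protocol 4.5.2.1 does let diuretics be reduced once targets are met, so output could fall in that wait, but nothing shows that it does. Higher losses still would need a course shorter than the two-day minimum.

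**Reach.** Weaning is worded permissively, and the last available reading may precede it if the cath-lab value is missing. Not every patient is affected.

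**Consequence.** This is a single-arm feasibility study. Its sample size was not statistically derived, and urine output has no test or success threshold. Individual cumulative plots and listings run to retrieval, so the tail stays visible. This limits the importance of the point but does not settle which window the endpoint uses.

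**Conclusion.** The point holds at modest size. SAP 7.8.3.1 and 7.14 measure a longer window than protocol 3.3.3 and SAP 7.8.3 define. In patients who are weaned and have the cath-lab reading, reduced-speed hours, and up to 12 h at full speed after the target-met assessment, are counted as therapy.

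At the minimum wean with no wait, the share is about 6% after 48 h and about 2% in a 7-day run. It exceeds this materially only if the wait is counted too or the wean is longer. The direction is towards no effect if output falls in those hours; the documents contain no urine data with which to confirm that. Whether a better cut-off is available for every patient depends on the CRF. The inconsistency between the two SAP sections needs no assumption.

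**What to change.** In SAP 7.8.3.1 and 7.14, define the end of the on-therapy interval in this order:

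1. the protocol 4.5.3 fluid reading (target met or therapy ineffective), where entered;
2. otherwise the last fluid reading at or before the first speed reduction of the final wean, so that earlier reductions for hemolysis or safety do not close the window;
3. if there was no wean or no such reading, the last pre-retrieval reading, with the patient flagged.

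Report the present full pre-retrieval window as a sensitivity row and the wean-to-retrieval rate as a descriptive row. Align SAP 7.8.3 with 7.8.3.1, and state in 7.14 exactly what the CRF does and does not collect at the target-met timepoint.

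The cost is SAP wording and a somewhat more complex derivation, using readings that the protocol already requires. The CRF must be checked for those readings and for a way to identify the final wean. Rule 2 removes weaning hours but can leave the pre-wean wait in the window, and the fallbacks mean that not all patients share one definition. The flag and the sensitivity row make that visible.
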